Breathalyzer measurement of BAC or BrAC requires frequent repeated measures that may be too burdensome and invasive for participants [14-17]. In contrast, TAC sensors provide a mostly passive and non-invasive approach for continuously monitoring alcohol exposure. TAC sensors are worn on the ankle or wrist and measure the 1% of alcohol that is eliminated through the skin via insensible perspiration or sweat [16, 18-21]. One limitation of TAC is that it is not quantitatively equivalent to BAC or BrAC. TAC reflects an individual's relative alcohol exposure, whereas BAC/BrAC reflect absolute alcohol exposure, which provides actionable information about a person's likely level of cognitive and physical impairment due to alcohol use [18, 22]. Unfortunately, there are currently no reliable methods for directly estimating BAC from TAC, due to the variety of factors that can impact individual differences in TAC (e.g., sex, age, fat-free mass, skin temperature) [15, 21-26]. Translating TAC to BAC/BrAC is necessary prior to leveraging wearable TAC sensors to provide actionable knowledge to inform just-in- time harm reduction interventions. The most unobtrusive and user-friendly TAC sensor currently in use is the BACtrack Skyn (Skyn). The Skyn is a small, lightweight wrist-worn sensor that collects TAC data every 20 seconds and that participants are comfortable and willing to wear across extended time periods in natural settings [14-17, 22, 27-30]. The few studies testing the Skyn under controlled laboratory conditions suggest that Skyn TAC values strongly correlate with BrAC [15] and can be used to estimate BAC at low or moderate BAC levels [31]. However, it is often infeasible and unethical to dose participants in laboratory settings to the excessive levels they dose themselves in natural settings. Additionally, laboratory studies preclude examining whether TAC values predict next-day alcohol-related harms, such as hangovers or blackouts. While two studies have compared the Skyn to another commonly-used TAC sensor in natural settings and found moderate-to-strong correlations between the sensors, [27, 30] we are unaware of any studies comparing the Skyn to BAC or BrAC in natural settings or of any studies examining TAC relative to BrAC as a predictor of volume of consumption and alcohol-related harms (e.g., sickness, hangover). As such, it remains unclear whether correlations between Skyn TAC values and BrAC captured in controlled laboratory settings translate to alcohol use in real-world settings or whether TAC values perform similarly to BrAC in predicting next-day alcohol-related harms [17, 22, 27, 31].

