Participants will receive a beverage containing either a dietary supplement (10g Fibersol®-2 mixed with water and aspartame sweetener for taste + 725mg decaffeinated green tea extract capsule) or a calorically matched placebo supplement (Aspartame sweetener mixed with water + aspartame capsule) counterbalanced at two separate visits. Forty-five minutes after the dietary supplement, the second blood sample is taken. Next, a priming drink (calculated to achieve 30mg% BAC) is administered to stimulate craving for alcohol [66, 67]. Drinks will consist of 40 proof vodka and a sugar-free cranberry juice mixer at a 1:5 ratio. Doses are calculated to achieve target BACs based on sex and body weight using formulas established in prior research [68]. Fifteen minutes after the priming drink, a novel alcohol-specific satiety questionnaire will be administered followed by alcohol incentive motivation tasks (alcohol purchase task; APT [69], dot probe attentional bias to alcohol-related stimuli), additional validated alcohol subjective response questionnaires (Drug Effects Questionnaire; DEQ[70], Biphasic Alcohol Effects Scale; BAES [71], Alcohol Urge Questionnaire; AUQ [72], Subjective Effects of Alcohol Scale; SEAS [73]), *hunger, fullness, and satiety* visual analogue scale (VAS) items, a BACtrack S80 BrAC measure, and a fingerprick blood sample.

Alcohol-specific satiety paced drinking procedure

Then over a 2-hour period, 5 additional mini-drinks (calculated to achieve an estimated BAC increase of 10mg% each or placebo) are administered with 15 min absorption time between each drink to reach an estimated maximum BAC of 60-70mg%, reflecting a moderate level of alcohol exposure (80mg% is the conventional cutoff for “binge” exposure). Participants have 3 minutes to finish each drink (Average volume of a drink, alcohol+mixer at a 1:5 ratio is 8/5oz for a man/woman). This paradigm is designed to approximate a natural drinking pace, while controlling for the BAC during subjective satiety assessment. The control session will control for expectations of increased satiety with subsequent drinks. Control drinks contain cranberry juice with an alcohol mask (rim sprayed with vodka) matched in total volume to the alcohol drinks. Participants will be told that all drinks contain alcohol. Subjective response questionnaires are repeated 15 minutes after each drink. BACtrack S80 BrAC measures are repeated every 15 minutes.

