After the paced drinking procedure, a final fingerprick blood sample will be taken and participants will remain in the lab until their BAC reaches 0mg% at which point they will be either dismissed. At the end of the second lab session, participants will receive instructions on using the Skyn and BACtrack S80 devices, using the Skyn app for syncing Skyn data and the LifeData app for completing drinking bout EMA surveys and morning surveys about past day alcohol use and consequences.

Remote assessment

During the 7-day naturalistic study, participants will be asked to wear the Skyn for 24 hours/day for 7-days (except when bathing or swimming). On days when participants choose to drink they will initiate drinking bout surveys via smartphone by indicating they have started drinking, after which they will be prompted to provide a BrAC reading once every 20-minutes throughout the drinking bout and for up to 1-hour after the drinking bout ends. Every 60-minutes participants will also self-report alcohol amount and subjective intoxication during the drinking bout. Importantly, participants will be informed that they are not expected to change their drinking behaviors during the study and compensation is not contingent on self-reports or breathalyzer readings during drinking bouts. Participants will complete daily morning surveys about past day alcohol use and consequences and evening surveys about daily pain and stress.

After the 7-day protocol, participants will return their devices to the PI's lab and report past 7-day drinking behaviors (timeline follow-back; TLFB) and drinking consequences (Brief Young Adult Alcohol Consequences Questionnaire, Importance of Consequences of Drinking short-form) and undergo a DEXA scan. Participants will be compensated upon device return with up to \$240 (\$20 for baseline surveys, \$50 for lab visit one, \$50 for lab visit two, \$70 for all 7-day EMA study procedures, \$10 for device return, \$10 for follow-up questionnaires, \$10 for DEXA scan, and \$10 study completion bonus).

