BACtrack Skyn TAC Monitor: The BACtrack Skyn is a small, lightweight wrist monitor that measures alcohol exposure through the 1% of alcohol transmitted through perspiration (i.e., transdermal alcohol concentration). The device wirelessly syncs to the Skyn app on the participant's iPhone to collect TAC data every 20 seconds. Alcohol exposure is detected with an average delay of 35.6 minutes [84]. The following outcomes are derived from TAC data: *drinking intensity* (peak TAC and area under the curve [AUC]), *drinking duration* (hours with TAC >0 µg/L air), *rise rate* (average rate of all ascending point-to-point TAC values), and *fall rate* (average rate of all descending point-to-point TAC values).

BACtrack S80 BrAC Monitor: The BACtrack S80 is a portable, battery-operated professional breathalyzer that measures the percentage of alcohol in a person's breath (i.e., BrAC). Participants capture BrAC within seconds after following a series of automated instructions provided by the S80 and breathing into the mouthpiece. Participants will report their S80 readings in the EMA surveys. The outcomes derived from the BrAC data are the same as those described above for TAC data.

Behavioral tasks:

The alcohol purchase task (APT) measures the hypothetical behavioral economic demand for alcohol at 14 different price points. This measure is sensitive to the reinforcing effects of alcohol, and predictive of real-world alcohol consumption [69]. The following outcomes are derived from the APT: APT-intensity (consumption when drinks were free); APT-breakpoint (the first price at which consumption was suppressed to zero); and APT-Omax (maximum alcohol expenditure) [69]. The task takes no more than 5 minutes to complete and is administered on REDCap

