8. STATISTICAL CONSIDERATIONS

8.1 SUMMARIZE THE STATISTICAL ANALYSIS STRATEGY FOR EACH SPECIFIC AIM

Descriptive statistics (e.g., frequency, mean, standard deviation, variance, range) will be generated for all study variables. Continuous study variables will also be examined for normality and homogeneity of variances using visual inspection methods (e.g., histograms, box plots, residuals, Normal Q-Q plots) and quantitative methods (Shapiro-Wilk test). If these assumptions are violated, the continuous study variables will be transformed, as necessary (e.g., log transformation). Exploratory analysis of the association between participant characteristics and study outcomes will be tested using Pearson correlation coefficients, chi square, and analysis of variance.

To analyze study aims 1 and 2, multi-level regression models will examine the within-person correlations between TAC and BrAC measurements, including peak TAC/BrAC and area under the TAC/BrAC curves (AUC). Models will test within-person correlations between TAC and BrAC during the in-lab alcohol administration and naturalistic drinking bouts and will investigate whether correlations differ across conditions. Multi-level models will test TAC predicting drinks consumed and the odds and frequency of alcohol-related harms (e.g., hangover, missed classes), and will examine whether BrAC accounts for additional variance in those outcomes. Person-specific algorithms for predicting BrAC from Skyn TAC data will be developed using a backwards step-wise multiple linear regression approach starting with Skyn TAC data as the primary predictor and adding relevant covariates (e.g., fat-free mass, skin temperature) that result in statistically significant and/or clinically meaningful improvements to the model.

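### The BrAC-from-TAC algorithm is called person-specific, but its step-wise ordinary regression cannot estimate fat-free mass per person or handle repeated readings if pooled, and it has no out-of-sample check

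*Combined protocol and SAP*

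**What the plan says.** Section 8.1 of the combined protocol and SAP treats the main Aim 1 and 2 analyses as multi-level. For Aim 1, "multi-level regression models will examine the within-person correlations between TAC and BrAC measurements"; the Aim 2 models for drinks and harms are also multi-level. The same paragraph then changes method for the algorithm that predicts BrAC from TAC. The algorithms are labelled person-specific and are to be developed by a "backwards step-wise multiple linear regression approach starting with Skyn TAC data as the primary predictor and adding relevant covariates", with fat-free mass and skin temperature as examples. Covariates enter if they are ones "that result in statistically significant and/or clinically meaningful improvements to the model". No numerical threshold and no closed list of candidates is given.

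Fat-free mass comes from a single DEXA scan (Section 4.1, Overall Design), which says it will be a covariate in later analyses without naming this model. Section 2.2 gives reasons to expect such covariates to matter: "the variety of factors that can impact individual differences in TAC (e.g., sex, age, fat-free mass, skin temperature".

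On timing, Section 4.3 says of the Skyn: "Alcohol exposure is detected with an average delay of 35.6 minutes". In the laboratory, "BACtrack S80 BrAC measures are repeated every 15 minutes". In the remote week, after participants report that they have started drinking, "they will be prompted to provide a BrAC reading once every 20-minutes throughout the drinking bout".

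No section describes a random effect or clustered error for this algorithm, a hold-out sample, cross-validation or bootstrap, a measure of prediction error, or a rule for pairing TAC with BrAC. The one device validation step, in Section 4.1, concerns the light-based finger sensor.

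**The concern.** The sentence cannot be carried out as written. If person-specific means one regression per participant, fat-free mass is constant within each fit and has no estimable coefficient, although it is a named candidate. If readings are pooled so that fat-free mass can enter, multiple linear regression treats repeated readings from one person as independent, and the p-value for a person-level covariate is too small. The selection direction is also contradictory: backward selection removes terms, whereas the text starts from TAC and adds them.

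Under either reading, the only accuracy available from the plan is the fit in the data used to build the model. Section 2.2 says that TAC must be translated to BAC or BrAC before wearables can give actionable information. The quantity that matters is therefore error in a new user or a new bout, and the plan does not estimate it.

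**Working it through.** **Inputs from the documents.** 42 completers (Section 4.2, Participants); one fat-free mass value per person; average TAC delay 35.6 minutes; BrAC every 15 minutes in the laboratory and every 20 minutes in the field. The plan states no accuracy or retention figure to reproduce.

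**Assumptions.** m = 10-20 paired readings per person, residual ICC 0.1-0.5, TAC alone giving R2 of 0.5, retention at p<0.05. None of these is in the documents, so ranges are shown.

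**1. Retention of a null person-level covariate, readings pooled.** For a covariate constant within person, the variance of its coefficient is inflated by 1 + (m-1)×ICC. The chance that ordinary regression keeps it when it adds nothing is 2×[1 - Φ(1.96/√(1+(m-1)×ICC))].

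| m | ICC 0.1 | ICC 0.3 | ICC 0.5 |
|---|---|---|---|
| 10 | 0.155 | 0.308 | 0.403 |
| 20 | 0.250 | 0.449 | 0.545 |
| 40 | 0.376 | 0.582 | 0.665 |

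For example, m = 20 and ICC = 0.5 gives 1 + 19×0.5 = 10.5; 1.96/√10.5 = 0.605; two-sided probability 0.545. Simulated backward elimination with fat-free mass and skin temperature, both null (1,500 replicates per setting, m = 10-20), kept fat-free mass in 17.0-54.6%. Skin temperature that varied only within person was kept in 4.1-5.7%, so there was no inflation. When half its variance lay between people, it was kept in 10.3-44.7%.

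**2. Overstatement of R2 without an out-of-sample check.**

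- Readings pooled, R2 in the sample minus R2 in 400 new people: 0.006-0.024 with the two named candidates, and 0.010-0.050 with four (fat-free mass, sex, age, skin temperature).
- One summary value per person: 0.044 with two candidates, 0.056 with four. Clustering does not arise here.
- One model per person (TAC plus skin temperature): 0.518 - 0.347 = 0.171 at 10 readings; 0.505 - 0.435 = 0.070 at 20.

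**3. Time alignment, for point-level prediction only.** 35.6/15 = 2.4 laboratory intervals; 35.6/20 = 1.8 field intervals. Take a noise-free laboratory curve peaking near 66 mg% (assumed: elimination 15 mg% per hour, absorption constant 10 minutes, drink contributions set to reach that peak). With TAC shifted by exactly 35.6 minutes, same-clock pairing lowers R2 from 1.00 to 0.68 over the whole curve, but only to 0.93 over the first three hours and 0.97 on the rising limb. The loss comes mainly from mixing rising and falling limbs.

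**4. Does the proposed method work?** With a random participant intercept and TAC slope, the mixed-model test rejected a null fat-free mass effect in 4.4-6.2% (500 replicates in each of six settings). Leave-one-participant-out R2, with selection repeated in each fold, was within 0.01 of R2 in new people in all four settings tried (60 replicates): 0.462 against 0.459, 0.476 against 0.466, 0.521 against 0.519 and 0.500 against 0.501. The in-sample values were 0.498, 0.495, 0.555 and 0.524.

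**The case against.** The strongest reply is that the plan says person-specific. If one model is fitted to each participant, clustering between people does not arise, and the missing random effect is not in itself a fault. That is correct. What remains is the conflict with fat-free mass and the larger optimism of small per-person fits.

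A second reply is that the retention figure supposes that fat-free mass has no effect, whereas Section 2.2 lists it among factors affecting TAC, and Section 4.1 may mean that it is forced in. This also stands: if it is forced in, retention is moot. A reader might infer that the selected covariates would be noise. The documents do not support that, and the figure shows only that the selection test would be unreliable under pooling.

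A third reply concerns the delay. On the Section 4.3 targets (30 to 60-70 mg% over about two hours, taken as linear), 35.6 minutes corresponds to 35.6×30/120 = 8.9 to 35.6×40/120 = 11.9 mg%. A reader might take this as prediction error, but on a linear rising limb a fixed lag is a constant offset that the intercept absorbs. The stated delay is also an average delay in detection, not a uniform shift of the curve. If peak or AUC enters the algorithm, alignment matters much less, and the plan does not say which form of TAC is used.

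Finally, the algorithm is not one of the five aims, the study is a pilot, and no accuracy claim or deployment is planned. That limits the weight of the point without removing it.

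**Conclusion.** The point holds in a limited form. The algorithm sentence conflicts with itself on the unit of analysis, and neither reading gives sound covariate selection together with an honest accuracy figure. If readings are pooled, a null fat-free mass term is kept in about 15-55% of cases instead of 5%, and R2 is overstated by about 0.01-0.05. If one model is fitted per person, fat-free mass cannot be estimated and R2 is overstated by about 0.07-0.17. These harms belong to different readings and must not be combined; optimism under pooling is small. All sizes rest on the assumed readings per person, ICC and p<0.05 rule. The alignment gap applies only to point-level prediction.

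A reader might infer that the Aim 1 and 2 results are compromised. They are not: those tests are multi-level, and this algorithm is a secondary product. The change is worth making before analysis, with moderate confidence in the sizes.

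**What to change.** State whether the algorithm is fitted per person or pooled, and then:

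1. If readings or bouts are pooled, replace step-wise ordinary regression with a linear mixed model having a random participant intercept and TAC slope, and a pre-listed covariate set (fat-free mass, sex, age, skin temperature). State whether fat-free mass is forced in. This also removes the conflict over selection direction.
2. Report accuracy as cross-validated prediction error, repeating covariate selection and any lag choice inside each fold. Leave out one participant at a time, with fixed-effect predictions, if the algorithm is for new users. Hold out bouts or sessions within person if it is calibrated to each person.
3. For point-level prediction, fix the TAC-BrAC lag in advance or estimate it in the training data only. Section 4.3 ends field BrAC prompts at most one hour after a bout, so the lag also determines which field pairs exist.
4. Do not present covariates kept by cross-validation as shown to matter; use the mixed-model test for that.

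The cost is SAP wording and programming on data already collected. The drawbacks should be stated. Reported accuracy will look less favourable. Cross-validated selection kept at least one null covariate in 48-60% of a small simulation (four candidates, 60 replicates). Leaving out one bout is pessimistic when a person has only two: mean squared error 1.57 against 1.26 in a new bout, compared with 1.24 against 1.18 for three bouts (assumed bouts of 10 readings, serial correlation 0.5).

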3. OBJECTIVE AND OUTCOME MEASURES

Aim 1: Identify the correlations between transdermal alcohol concentration (TAC) and breath alcohol concentration (BrAC) in controlled laboratory and natural settings and compare correlations across settings.

- Outcomes measures: BrAC using the BACtrack S80 and TAC readings using the BACtrack Skyn monitor and light-based finger monitor during laboratory alcohol drinking sessions and a remote assessment period.

Aim 2: Compare TAC and BrAC as predictors of self-reported number of drinks consumed and the odds and frequency of alcohol-related harms in natural settings.

- Outcome measures: BrAC and TAC readings, self-reported number of drinks and alcohol related harms measured using a mobile app questionnaire (LifeData app).

Aim 3: Model individual differences in alcohol-specific satiety using self-report and a paced-drinking alcohol administration laboratory model.

- Outcome measures: Alcohol specific satiety questionnaire, BrAC readings.
- Secondary measures: Self-report alcohol subjective effects (stimulation, sedation, craving), behavioral economic demand for alcohol, attentional bias for alcohol related cues.

Aim 4: Assess the effect of a dietary supplement on satiety to alcohol

- Outcome measures: Blood plasma GLP-1 levels samples during lab sessions via venipuncture before and after supplement administration, alcohol-specific satiety questionnaire

Aim 5: Assess the effect of alcohol exposure on HMBG-1 marker of inflammation

- Outcome measures: Blood plasma levels of HMBG-1 will sampled during lab sessions via fingerprick at timepoints before alcohol administration, 30 minutes after an initial priming drink, and after the final drink.

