To analyze study aim 3, multi-level regression models will be used to assess within-person changes on repeated measures along with between-person individual differences. A linear growth curve model will be used to test the hypothesis that alcohol-specific satiety increases with time and additional drinks. Timepoint (1-6) and drug (alcohol or placebo) will be included in the model as within subject factors. Compared to placebo, alcohol is predicted to be associated with higher rates of change (slope) in satiety. Next, AUDIT will be included as a continuous predictor of slope in the model to test the hypothesis that participants with fewer alcohol dependence symptoms (lower AUDIT scores) report reduced satiety. Finally, subjective craving scores (Alcohol Urge Questionnaire; AUQ) from each timepoint will be included in the model. The effect of satiety over time is expected to remain significant after controlling for craving. Alcohol-specific satiety is expected to be negatively associated with measures of reward and incentive motivation for alcohol (BAES, APT, Dot Probe). Outcomes from each of these measures will be included in separate multi-level models with satiety scores as the primary dependent measure and timepoint (1-6) and drug (alcohol, placebo) as within-subject factors to determine the effect of additional dependent measures on within-person change in alcohol specific-satiety over time (slope).

To analyze aim 4, a repeated measures analysis of variance (ANOVA) will be used to assess the effect of a dietary supplement on alcohol-specific satiety in a 2(alcohol, placebo) x 2(timepoints) design. It is

predicted that compared to placebo, a GLP-1 stimulating dietary supplement will increase alcohol-specific satiety.

To analyze aim 5, linear regression will be used to assess the association between HMGB1 levels as a function of BrAC during the laboratory alcohol sessions. Data processing and analyses will be completed in R and SPSS.

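### No Aim 3 satiety model uses measured BrAC, so an AUDIT difference in satiety slope cannot be told apart from a difference in achieved BAC rise

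*Combined protocol and SAP*

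**What the plan says.** Section 8.1 sets out the Aim 3 models term by term. The growth model for satiety is described as follows: "Timepoint (1-6) and drug (alcohol or placebo) will be included in the model as within subject factors". Next, "AUDIT will be included as a continuous predictor of slope in the model", and then "subjective craving scores (Alcohol Urge Questionnaire; AUQ) from each timepoint will be included in the model". For BAES, APT and Dot Probe, "Outcomes from each of these measures will be included in separate multi-level models with satiety scores as the primary dependent measure", again with timepoint and drug. None of these models has a BrAC term. Elsewhere in Section 8.1, BrAC is analysed for Aims 1 and 2 and is the exposure variable for HMGB1 in Aim 5.

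Section 3 nevertheless gives, for Aim 3, "Outcome measures: Alcohol specific satiety questionnaire, BrAC readings". Section 4.3 collects the data: "BACtrack S80 BrAC measures are repeated every 15 minutes", with satiety rated again 15 minutes after each drink. On dosing it says "Doses are calculated to achieve target BACs based on sex and body weight using formulas established in prior research", and it describes the paced procedure as approximating natural drinking "while controlling for the BAC during subjective satiety assessment". It describes no step that adjusts a drink to the BrAC just measured.

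**The concern.** Aim 3 is about individual differences in satiety to alcohol, and the AUDIT term is its main between-person test. Timepoint counts drinks. It is the same for everyone, so it cannot represent how far each person's BAC actually rose. If AUDIT is related to that rise, the AUDIT-by-slope test mixes sensitivity to alcohol with exposure to it. The control session does not remove this, because the exposure difference arises only where alcohol is given.

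What is at stake is how the AUDIT result is read. A flatter slope in one group might mean less satiety per unit of alcohol, or less alcohol in the body per drink. The reading that would distinguish the two is already being taken, and it has no role in the Aim 3 analysis.

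**Working it through.** **1. The plan's own exposure figures (Section 4.3).** The priming target is 30 mg%, followed by five mini-drinks of 10 mg% each. The nominal sum is 30 + 5 x 10 = 80 mg%. The expected peak is 60-70 mg%, so the plan implicitly allows 10-20 mg% to be lost over the two hours. The rise from priming is 30-40 mg%, or 30/5 = 6 to 40/5 = 8 mg% per mini-drink. Around the midpoint of 7 this is +/-1/7 = +/-14%. The documents do not say whether the band describes differences between people or uncertainty about the average.

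**2. What would have to be true for bias.** Two quantities matter: the between-person spread of BAC rise per drink, and its correlation with AUDIT. Neither is in the documents, so both are assumed below. N = 42 comes from Section 8.2. The point does not change the sample size.

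**3. Simulation with the BAC rise specified directly.** There are 42 people, six timepoints, the alcohol session only, and no direct AUDIT effect on satiety. BAC starts at 30 and rises by 7 x (1 + CV x u) mg% per drink, where u is standard normal and correlates r with AUDIT. Satiety = (0.3/7) x BAC, plus a person intercept (SD 1), a person slope (SD 0.1) and residual error (SD 0.5). Each person's satiety slope is regressed on AUDIT, with a two-sided 5% test and 10,000 runs per cell. Rejection rates without BrAC:

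| CV of BAC rise | r = 0.2 | r = 0.3 | r = 0.5 |
|---|---|---|---|
| 7% (band taken as +/-2 SD) | 5.3% | 5.8% | 7.1% |
| 14% (band taken as +/-1 SD) | 5.9% | 8.3% | 13.3% |
| 30% (wider than the band suggests) | 9.5% | 15.1% | 37.0% |

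At r = 0 the rate is 4.7-5.0% at all three spreads. With each person's BAC slope added, it is 4.7-5.3% in every cell of the table.

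**4. Simulation with elimination specified.** Net rise per drink is 10 mg% minus elimination rate x cycle length. Volume of distribution has a CV of 10%, satiety per unit BAC has a CV of 30%, and slope noise has SD 0.5. AUDIT correlates 0.2-0.4 with elimination rate. Section 4.3 permits two cycle lengths: 120/5 = 24 minutes, or 3 + 15 = 18 minutes. Mean elimination was set so that the peak falls inside the band:

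- 24 minutes (0.4 h), mean 7.5 mg%/h: 10 - 0.4 x 7.5 = 7 mg% per drink, peak 30 + 5 x 7 = 65 mg%. Rejection is about 6-8% at SD 1.25 mg%/h and 8-16% at SD 2.5.
- 18 minutes (0.3 h), mean 10 mg%/h: 10 - 0.3 x 10 = 7 mg% per drink, peak 65 mg%. Rejection is about 6-10% at SD 2 mg%/h and 7-15% at SD 3.

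Steps 3 (CV 7% and 14%) and 4 together give about 5-16% at correlations of 0.2-0.4.

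**5. Direction.** Section 8.1 predicts that lower AUDIT goes with reduced satiety, hence a steeper slope at higher AUDIT. If higher AUDIT goes with faster elimination, BAC rises less per drink at higher AUDIT and the satiety slope is flatter. That is the opposite sign. This bias would work against the predicted effect as well as create false findings the other way.

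**The case against.** Four arguments on the other side have weight.

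First, dosing by sex and weight narrows differences in achieved BAC, and Section 4.3 calls its BAC figures estimated. Section 4.1 also promises DEXA fat-free mass as a covariate in later analyses, to allow for elimination rate. Both are real mitigations but only partial. Section 4.1 does not name Aim 3, Section 8.1 mentions fat-free mass only for predicting BrAC from TAC, and fat-free mass is a proxy for a quantity that is measured directly here.

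Second, satiety per drink is a legitimate quantity. Section 8.1 states the hypothesis in terms of time and additional drinks, and achieved BAC may lie on the path from AUDIT to satiety. This stands, and it is why the planned model should be kept.

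Third, BrAC and timepoint rise together in the alcohol session, so a model with BrAC separates them poorly. This also stands as a cost of the added model.

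Fourth, nothing in the documents shows that AUDIT correlates with BAC rise. Excluding AUDIT scores of 20 or more and severe AUD (Section 5.2) limits the range over which such a link could act. At zero correlation there is no inflation.

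A reader might go further and infer that exposure differs between people by a large multiple, or that a significant AUDIT term would probably be an artefact. The documents do not support either. Such results need, for example, mean elimination of 15 mg%/h on a 24-minute cycle. That gives 10 - 0.4 x 15 = 4 mg% per drink and a peak of 30 + 5 x 4 = 50 mg%, below the plan's 60-70 mg%.

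**Conclusion.** The omission is plain from the text: BrAC is an Aim 3 outcome measure, is recorded alongside the satiety ratings, and enters no Aim 3 model. The claim in Section 4.3 to control BAC holds for nominal dose only. As written, the AUDIT-slope test cannot separate sensitivity from exposure.

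The size is unknown. With assumptions centred on the plan's own peak, the false-positive rate is about 5-16% against a nominal 5%, which is modest. It would be larger only if BAC rise varied more between people than the 60-70 mg% band suggests, or if AUDIT tracked it more closely than 0.4. All of this rests on assumed correlations, spreads and satiety variances. The direction is also conditional: if higher AUDIT means faster elimination, the bias runs against the written hypothesis and could hide it. This is a cheap improvement to the plan, not a defect that invalidates Aim 3.

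**What to change.** Keep the planned timepoint-by-drug and AUDIT models unchanged. In Section 8.1, pre-specify one further model for the alcohol session:

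- Outcome: satiety at each rating.
- Predictors: the person's mean BrAC, the within-person deviation of time-matched BrAC from that mean, AUDIT, and AUDIT x within-person BrAC. The last term tests whether AUDIT moderates the satiety-BrAC slope.
- A stated rule for matching BrAC readings to satiety ratings, and a statement of whether timepoint stays in this model.

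Report the AUDIT effect with and without BrAC, side by side, and label the adjusted one as the effect at equal BrAC. Reword Section 4.3 to say that nominal dose, not achieved BAC, is controlled. State whether the fat-free-mass covariate of Section 4.1 applies to Aim 3.

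The cost is some wording and one model on data already collected, with no new visits, samples or participants. The plan should state the downsides: BrAC is measured with error, it is collinear with timepoint, and it may be a mediator. These are the reasons for reporting both versions. Specifying the model now keeps the BrAC-adjusted result from being post hoc.
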